1.0 Background

Hepatic fibrosis refers to the interstitial or extracellular matrix accumulation or “scaring” after either acute or chronic liver injury. Vast majority of patients worldwide are associated with chronic hepatitis due to hepatitis B and C virus infection, steatohepatitis associated with chronic alcoholic use, and non-alcoholic steatohepatitis due to obesity, diabetes mellitus, and drugs. However, hepatic fibrosis can occur virtually from any acute or chronic liver disease that presents with hepatobiliary inflammation, which undergoes the steps of steatosis fibrosis, and cirrhosis [1, 2]. Liver cirrhosis, the end-stage of progressive fibrosis, is a major cause of morbidity and mortality in America.

In oncologic patients, there are several predisposing factors to hepatic inflammation that can lead to fibrosis: A few among these are chemotherapeutic agents, such as irinotecan or oxaliplatin, multiple transfusions in patients with hematologic malignancy, graft-versus host disease and hepatic veno-occlusive disease following bone marrow transplantation. The neoadjuvant chemotherapy with irinotecan or oxaliplatin is known as a predisposing factor to hepatic steatosis or steatohepatitis, which could affect the post-surgical morbidity negatively in those who are undergoing the hepatic resection [3-5]. Multiple transfusion induced hepatic hemosiderosis is a known risk factor for hepatic fibrosis. Certain tumors such as metastasis from breast cancer often heal with surrounding fibrosis of the liver tissue. Detection of recurrence can be challenging within the fibrotic liver using conventional cross-sectional images.

Typically, fibrosis requires years or decades to become clinically apparent but it can develop in months in children with biliary atresia, drug induced liver disease, or viral hepatitis associated with immunosuppression.

The parenchymal liver disease can be evaluated non-invasively using conventional CT, MR imaging, and ultrasound (US), primarily on the basis of morphological changes. However, once morphological change is recognizable by these imaging techniques, the liver disease is often advanced to the irreversible stage of cirrhosis with the concomitant risk of debilitating or possibly life-threatening complications.

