3.0 Patient Eligibility

The study will have 2 groups of patients with a total of 30 patients each.

A total of 30 patients (Group 1) with biopsy proven or clinically suspected advanced parenchymal liver disease (fatty liver, fibrosis, and cirrhosis) will be recruited from VA Medical Center in Houston. An additional 30 patients (Group 2) will be recruited among those who are registered at MDACC and who are suspected to have hepatic damage, hepatic steatosis, hepatitis, hepatic fibrosis or cirrhosis clinically or radiographically. The number of accrual in Group 2 will be adjusted as needed upon completion of data analysis for the first 30 patients.

The patients recruited at MDACC will be approached by either the Diagnostic Imaging faculty or Research Staff, including research nurses and research coordinators for their consent prior to their procedure. During the consenting process patients will be educated and consented for their research participation in this study.

Inclusion criteria:

Group 1

1. Biopsy proven or clinically suspected advanced parenchymal liver disease
2. Core biopsies performed within 1-month* of MRI/MRE
 3. No treatment affecting the status of liver between MRI/MRE and post-imaging biopsy
4. Signed consent

*The interval between the biopsy and MRI/MRE is allowed for up to 8 weeks if the liver condition is thought to be stable during this time per a collaborating hepatologist.

Group 2

1. Clinically or radiographically suspected liver damage, hepatic steatosis, hepatitis, hepatic fibrosis or cirrhosis
2. Surgical or core biopsy scheduled within 4 weeks* of MRI/MRE
3. Signed consent

*The interval between the biopsy and MRI/MRE is allowed for up to 8 weeks if the liver condition is thought to be stable during this time per the primary physician.

Exclusion criteria:

1. Claustrophobia
2. Contraindications for MRI
3. Unable to hold a breath
4. Ascites or other clinical or radiographical signs of portal hypertension

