2.2. Dual-echo 2PD MRI

Dual-echo 2PD MRI will be obtained in conjunction with the routine MRI of abdomen (if applicable) prior to administration of the intravenous contrast. The imaging parameters for a dual echo 2PD MRI include: TR 150 msec, TE 2.2 msec for out-of-phase and T2 4.7 msec for in-phase, flip angle 85 deg, slice thickness/gap 5-7/0.2 mm, matrix size 256x192, and the total scan time 20 seconds (a single breath-hold).

Once the images were obtained, a water-only (WO) and a fat-only (FO) images were generated for each slice automatically using the new post processing phase correction algorithm to correct the field heterogeneity [22].

3. Imaging analysis

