3.1 MRE

Overall quality of images will be evaluated based on the 1) line profile along the direction of wave propagation from each wave images, and 2) wavelength obtained by using a direct peak-to-peak measurement. The quality will be graded using a 5-point grading system: 1 being barely visible wave and 5 being the best.

The shear stiffness will be measured in kPa from the representative areas, up to 3 sites per patient.

3.2. 2PD MR images

The signal intensity (SI) will be measured on both fat (SI_f) and water (SI_w) images from the same area of region of interest. Then, % fat fraction (FF) will be calculated as $SI_f / (SI_f + SI_w)$ from FO and WO MR images.

4. Histopathological analysis

In Group I, core biopsies (at least 1.5 cm size) will be performed from up to 3 sites that are correlated with the representative areas for steatosis and fibrosis from MRE. The biopsy materials (slides) will be checked out by our collaborator at VAMC and will be hand-carried to our pathologist collaborator at MDACC for the study specific review. In group 2, surgical biopsies will be performed in the same manner.

The biopsy specimens will be evaluated and scored for hepatic steatosis, hepatic steatohepatitis, and fibrosis, based on the multiple histopathological features: 1) % of hepatocytes with macrovesicular steatosis (none, <5%, 5-33%, 33-66%, >66%), 2) location of macrovesicular steatosis (periportal, centrilobular, azonal, panacinar), 3) microvesicular steatosis (absent, present), 4) lobular neutrophilic and lymphocytic inflammation (per 200x field), 5) ballooning degeneration (score 0-1 = none, few, many), 6) acidophilic bodies (absent, present), and 7) Mallory's hyaline (absent, present), and 8) fibrosis (none, perisinusoidal, mild and moderate portal, mild and moderate periportal, bridging, cirrhosis) [23].

4.1. Hepatic steatosis will be graded using 4 point grading system; 0 being no steatosis, 1 being <30%, 2 being ≥ 30 - <60%, and 3 being $\geq 60\%$.

4.2. Hepatic steatohepatitis will be scored using 9 point grading system based on the sum of steatosis score (0 being <5%, 1 being 5-33%, 2 being >33-66%, 3 being >66%), lobular inflammation (score 1-3), and ballooning (score 0-2) [22].

4.3. Hepatic fibrosis will be graded using 5 point grading system, 0 being none, 1 being sinusoidal, 2 being mild to moderate portal, 3 being mild to moderate periportal, 4 being septal).

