4.4. Histopathological analysis will also be performed specifically for the underlying disease by the collaborating hepatic pathologist: e.g. in patients with hepatic iron overload the iron amount will be graded none, mild, moderate, and severe and in patients with GVHD the degree of bile duct injury and ductopenia will be evaluated.

5. The study will be terminated if we run into any unresolvable technical issues in data acquisition or unacceptable image quality to preclude the adequate analysis during the first 5 patient procedures.

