5.0 Statistical Analysis

1. Design

This is a pilot study designed to evaluate MRE and 2PD as alternatives to liver biopsy in evaluating fibrosis, steatohepatitis, and hepatosteatosis in patients with liver disease. There are two groups of patients in the study: patients in Group 1 will have advanced liver disease, while Group 2 will be for patients who undergo hepatectomy or core biopsy. We expect to enroll 30 patients into each group for a total of 60 patients. The number of accrual in Group 2 will be recalculated as needed upon completion of data analysis for the first 30 patients.

2. Analyses

For the first primary objective, the association between degrees of stiffness measured by MRE in kPa and histopathological grades of fibrosis and steatohepatitis will be assessed using Pearson correlation.

For the second primary objective, the association between % fat fraction measured by 2PD MR images and histopathological grade of hepatosteatosis and steatohepatitis will be assessed using Pearson correlation.

Because the above analyses assume that the fibrosis, steatohepatitis and steatosis grades are continuous variables, analyses will be repeated using rank correlation methods. In addition, as a secondary statistical analysis, we will perform ordinal regression analyses to evaluate the individual ability of MRE kPa and 2PD MRI %FF measurements and combination of both as covariates to predict grades of fibrosis, hepatosteatosis, and steatohepatitis for these patient populations.

3. Sample Size and Power

With 30 patients in each group, for each of the four correlations above, there will be 90% power to detect a correlation of at least 55% between the kPa or the %FF and the histopathological grade, assuming a two-sided alpha=0.05 level test for a non-zero correlation.

Although there are four separate primary comparisons being performed simultaneously, no correction will be made for the multiplicity of testing due to the pilot nature of the study. Each of the two primary objectives (two comparisons each) will have a Type I error rate (alpha level) of no more than 10%.1. Degree of stiffness measured from MRE in kPa will be correlated with histopathological grades of fibrosis and steatohepatitis.

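### Hepatic iron is graded but used in no analysis, although it can shift the two-echo fat fraction; a sensitivity analysis by iron grade would make the 2PD result interpretable

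*Combined protocol and SAP*

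**What the plan says.** **Iron in the population.** The Background (1.0) lists repeated transfusion among the predisposing factors in cancer patients and states: "Multiple transfusion induced hepatic hemosiderosis is a known risk factor for hepatic fibrosis". Section 4.0, item 4.4 adds histology specific to the underlying disease and gives iron as one of two examples: "in patients with hepatic iron overload the iron amount will be graded none, mild, moderate, and severe". None of the four exclusion criteria in Section 3.0 concerns iron; the only one about liver status is "Ascites or other clinical or radiographical signs of portal hypertension".

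**How %FF is obtained.** Section 4.0, item 2.2 gives the echo times as "TE 2.2 msec for out-of-phase and T2 4.7 msec for in-phase" (the second is evidently also an echo time). Water and fat images are produced "using the new post processing phase correction algorithm to correct the field heterogeneity". Item 3.2 then says: "The signal intensity (SI) will be measured on both fat (SI_f) and water (SI_w) images from the same area of region of interest". %FF is the fat signal divided by the sum of the fat and water signals. No correction for signal decay is mentioned.

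**How %FF is analysed.** Under Section 5.0, "the association between % fat fraction measured by 2PD MR images and histopathological grade of hepatosteatosis and steatohepatitis will be assessed using Pearson correlation". This is repeated with rank correlation. Secondary ordinal regressions use stiffness, %FF, or both as covariates. The iron grade appears in no correlation, regression, subgroup, sensitivity analysis or exclusion rule.

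**The concern.** A two-point Dixon method infers fat from the difference between the in-phase and out-of-phase signals. The in-phase echo is the later one here, so signal lost between the echoes looks like less fat. Iron speeds that loss. If patients differ in iron, their %FF values differ for a reason other than fat.

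The second primary objective asks whether %FF follows the histological grade, and the stated purpose is to validate the technique. If some livers carry much iron, a weak pooled correlation could mean that 2PD does not work, or only that it does not work when iron is present. A significant pooled correlation could equally hide failure in those patients. Section 5.0 as written cannot separate these cases, although pathology will already have graded iron in at least some patients.

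**Working it through.** **1. The plan's own figure.** Section 5.0 states 90% power for a correlation of 0.55 with n = 30 and two-sided alpha 0.05. By Fisher's z, power = Φ(atanh(0.55) × √27 − 1.96) = Φ(0.618 × 5.196 − 1.96) = Φ(1.253) = 89.5%. The figure reproduces, and the sample-size statement is not in question.

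**2. Inputs.** From the documents: echo times 2.2 and 4.7 ms (gap 2.5 ms) and the %FF formula. Assumed: one common single-exponential decay, fat image F = (IP − OP)/2, water image W = (IP + OP)/2, and a range of T2*. The documents give no T2*.

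**3. Formula.** For true fat fraction f, OP is proportional to (1 − 2f)·exp(−2.2/T2*) and IP to exp(−4.7/T2*). Then

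%FF = F/(F + W) = 0.5 × [1 − (1 − 2f) × exp(2.5/T2*)].

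**4. A liver with f = 20%.**

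| T2* | exp(2.5/T2*) | Apparent %FF |
|---|---|---|
| no decay | 1.000 | 20.0% |
| 25 ms | 1.105 | 0.5 × (1 − 0.6 × 1.105) = 16.8% |
| 10 ms | 1.284 | 0.5 × (1 − 0.6 × 1.284) = 11.5% |
| 5 ms | 1.649 | 0.5 × (1 − 0.6 × 1.649) = 0.5% |

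**5. When ranks change.** A shift common to all patients would not disturb their order; differences in decay do. A 20% liver falls below a 15% liver when the difference in decay rate exceeds ln(0.7/0.6)/2.5 ms = 0.1542/2.5 = 0.0617 per ms, about 62 per second. Against a liver with no decay, that means T2* below 1/0.0617 = 16.2 ms. Against one with T2* 25 ms (40 per second), it means a rate above about 102 per second, or T2* below about 9.8 ms. This holds with signed fat images. Because the ranks themselves move, rank correlation offers no protection.

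**6. Livers with equal iron.** With signed images the order is kept: at T2* 5 ms, zero fat reads −32.4% and 20% fat reads 0.5%. With magnitude images it can reverse: zero fat then reads 19.7%. The documents do not say which kind of image is used.

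**7. Illustrative effect on the correlation.** Simulation with n = 30, assumed grade frequencies of 25, 35, 25 and 15% for grades 0 to 3, fat fractions of 0, 8, 17 and 27%, iron independent of fat, and noise set so that power is about 90% without iron:

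| Iron-loaded patients | Decay rate (per s) | Power, signed | Power, magnitude |
|---|---|---|---|
| 3 of 30 | 60–150 | 90% | 84% |
| 3 of 30 | 150–300 | 84% | 75% |
| 6 of 30 | 60–150 | 90% | 77% |
| 6 of 30 | 150–300 | 81% | 55% |

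The effect runs from none to serious, depending on inputs that the documents do not supply.

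**The case against.** The other side has several good arguments. Iron overload enters the histology section only as an example, and the Background lists it among several predisposing factors. The objectives and inclusion criteria do not mention it, and no prevalence is given, so the number affected could be none or one. No T2* is given, and nothing links a histological grade of moderate or severe to a T2* value. The post-processing is described in one sentence, so the absence of a decay correction is inferred from silence. The study calls itself a pilot, and omitting an iron subgroup contradicts nothing in the plan. All of this stands and limits what can be said about size. It does not remove the gap: iron is graded, not excluded, and then unused.

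A reader might go further and take iron-loaded patients out of the primary correlation. The documents do not support that. Section 5.0 evaluates 2PD as an alternative to biopsy; dropping patients on a biopsy result because the technique is predicted to fail in them would favour the technique. It would also cost power: for r = 0.55, Fisher's z gives Φ(0.618 × √24 − 1.96) = 85.8% at n = 27 and Φ(0.618 × √21 − 1.96) = 80.9% at n = 24. A required iron covariate in the ordinal regressions is also hard to defend, since a sparse four-level factor with about 30 patients per group may not be estimable.

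**Conclusion.** The point holds as an inexpensive improvement, not as a flaw that invalidates the primary analysis. The textual part is firm: iron overload is anticipated and graded, not excluded, and enters no analysis. The physical part is conditional on single-exponential decay, the simple sum-and-difference reconstruction, and no decay correction. On those terms a 20% fat liver reads 16.8%, 11.5% or 0.5% at T2* 25, 10 or 5 ms, and patients with different iron can change places. The size of the effect in this trial is unknown and may be small.

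Three stronger readings are not supported:
- That the trial targets iron-loaded patients. They are anticipated, no more.
- That %FF generally runs backwards, with fat-free livers reading above fatty ones. At equal iron this needs magnitude images, which the plan does not specify; the 19.7% against 0.5% example also needs T2* of 5 ms, the shortest of the values tabulated in step 4.
- That the stiffness measurements are compromised in the same way. The MRE sequence is also gradient-echo, but nothing in the documents quantifies an effect, and item 3.1 already grades wave-image quality.

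The argument is about interpretation rather than power: with the iron grade unused, the trial cannot say whether a disappointing or a favourable %FF result applies to livers with iron.

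**What to change.** - **Section 5.0.** Keep the all-patient %FF correlations as primary. Prespecify a sensitivity analysis that repeats the Pearson and rank %FF correlations, for steatosis and for steatohepatitis, without patients whose iron grade is moderate or severe.
- **Reporting.** Show the %FF and steatosis grade of the moderate and severe patients separately. If the results with and without them differ, limit the 2PD validation conclusion accordingly.
- **Section 4.0, item 4.4.** Record the iron grade for every biopsy. As worded, only patients with iron overload are graded, so a grade of none would be assumed rather than observed for the rest.

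The cost is one extra histology field on slides already under review, a few lines of analysis text, and a smaller n with lower precision in the sensitivity analysis. That analysis should therefore be read as an estimate beside the primary result, not as a second test.

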5.0 Statistical Analysis

1. Design

This is a pilot study designed to evaluate MRE and 2PD as alternatives to liver biopsy in evaluating fibrosis, steatohepatitis, and hepatosteatosis in patients with liver disease. There are two groups of patients in the study: patients in Group 1 will have advanced liver disease, while Group 2 will be for patients who undergo hepatectomy or core biopsy. We expect to enroll 30 patients into each group for a total of 60 patients. The number of accrual in Group 2 will be recalculated as needed upon completion of data analysis for the first 30 patients.

2. Analyses

For the first primary objective, the association between degrees of stiffness measured by MRE in kPa and histopathological grades of fibrosis and steatohepatitis will be assessed using Pearson correlation.

For the second primary objective, the association between % fat fraction measured by 2PD MR images and histopathological grade of hepatosteatosis and steatohepatitis will be assessed using Pearson correlation.

Because the above analyses assume that the fibrosis, steatohepatitis and steatosis grades are continuous variables, analyses will be repeated using rank correlation methods. In addition, as a secondary statistical analysis, we will perform ordinal regression analyses to evaluate the individual ability of MRE kPa and 2PD MRI %FF measurements and combination of both as covariates to predict grades of fibrosis, hepatosteatosis, and steatohepatitis for these patient populations.

3. Sample Size and Power

With 30 patients in each group, for each of the four correlations above, there will be 90% power to detect a correlation of at least 55% between the kPa or the %FF and the histopathological grade, assuming a two-sided alpha=0.05 level test for a non-zero correlation.

Although there are four separate primary comparisons being performed simultaneously, no correction will be made for the multiplicity of testing due to the pilot nature of the study. Each of the two primary objectives (two comparisons each) will have a Type I error rate (alpha level) of no more than 10%.1. Degree of stiffness measured from MRE in kPa will be correlated with histopathological grades of fibrosis and steatohepatitis.

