2.0 Objectives

The purpose of the study is to validate the MRE and 2PD MRI technique using the new post-processing phase correction algorithm in evaluating chronic liver disease, specifically the hepatic inflammation, steatosis, steatohepatitis, hepatic fibrosis and cirrhosis in patients with biopsy proven or clinically suspected hepatic steatosis and/or fibrosis.

Primary goals:

1. To assess the association between the degree of stiffness as measured by MRE in kPa and histopathological grades of fibrosis and steatohepatitis
2. To assess the association between the % fat fraction (FF) measured from 2PD MRI and histopathological grade of hepatosteatosis and steatohepatitis.

Secondary goal:

To evaluate the roles of MRE and 2PD MRI in predicting the steatohepatitis and hepatic inflammation.

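### The plan aims to evaluate imaging as an alternative to biopsy, but its only powered criterion is a non-zero correlation, no interval or accuracy measure is planned, and the hepatic inflammation goal has no outcome of its own

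*Combined protocol and SAP*

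**What the plan says.** The aim is set in two places. Section 2.0 Objectives opens with "The purpose of the study is to validate the MRE and 2PD MRI technique". Section 5.0, item 1 (Design), describes a pilot that evaluates the two techniques as alternatives to biopsy: "This is a pilot study designed to evaluate MRE and 2PD as alternatives to liver biopsy in evaluating fibrosis, steatohepatitis, and hepatosteatosis".

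The two primary goals in section 2.0 are narrower. They read "To assess the association between the degree of stiffness as measured by MRE in kPa and histopathological grades of fibrosis and steatohepatitis" and "To assess the association between the % fat fraction (FF) measured from 2PD MRI and histopathological grade of hepatosteatosis and steatohepatitis". The secondary goal is "To evaluate the roles of MRE and 2PD MRI in predicting the steatohepatitis and hepatic inflammation".

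Section 5.0, item 2 (Analyses), plans Pearson correlations for the four primary pairs, a repeat with rank methods, and secondary ordinal regressions of the fibrosis, steatosis and steatohepatitis grades on kPa, %FF and the two together. Item 3 (Sample Size and Power) gives 90% power at a correlation of 0.55 with 30 patients per group, "assuming a two-sided alpha=0.05 level test for a non-zero correlation".

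Section 4.0, item 4.2, builds the steatohepatitis score as the sum of a steatosis score, a lobular inflammation score and a ballooning score.

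**The concern.** Rejecting a zero correlation shows that imaging and histology move together to some degree. It does not show how often imaging would place a patient in the right grade, which is what an alternative to biopsy has to do. The documents name no confidence interval for r, AUROC, sensitivity or specificity, kPa or %FF cut-off, agreement measure or minimum acceptable correlation. The ordinal regressions are the nearest thing to an analysis of prediction, but nothing says how their predictive ability will be summarised. If the plan is followed exactly, the report could list four significant correlations and leave the biopsy question without an estimate.

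The second gap is separate. Hepatic inflammation is named in the secondary goal, but it is not among the three grades that the regressions predict. It enters only through the steatohepatitis score, which also contains steatosis. A correlation of %FF with that score could come from steatosis alone and say nothing about inflammation.

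**Working it through.** **Inputs.** From section 5.0, item 3: n = 30 per group, design correlation 0.55, two-sided alpha 0.05, null value zero, stated power 90%. The AUROC model in steps 4 to 6 is an assumption, because the documents give no grade distribution and no accuracy benchmark.

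**1. The plan's own figure.** Fisher z power = Φ(atanh(ρ)·√(n−3) − 1.96).
- atanh(0.55) = 0.618 and √27 = 5.196, so power = Φ(3.213 − 1.96) = Φ(1.253) = 89.5%.
- With the bias term ρ/(2(n−1)) it is 90.4%. Simulating the Pearson t-test gives 90.3%.

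The stated 90% is reproduced.

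**2. What is enough to pass.** Critical r = t/√(n−2+t²). With t(0.975; 28 df) = 2.048, r = 2.048/√(28 + 4.196) = 0.361.
- Variance explained: 0.361² = 0.13.
- 95% CI: tanh(0.378 ± 1.96/5.196) = 0.00 to 0.64.
- For comparison, an observed 0.55 has 95% CI tanh(0.618 ± 0.377) = 0.24 to 0.76.

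**3. How often a weak marker passes**, by the formula in step 1:

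| True correlation | Chance of significance, n = 30 | n = 60 (if groups were pooled) |
|---|---|---|
| 0.30 | 36% | 65% |
| 0.40 | 60% | 89% |
| 0.50 | 81% | 99% |
| 0.55 | 89.5% | 99.7% |

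If the groups were pooled, the critical |r| would fall to 0.254 (6.5% of variance).

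**4. What such correlations mean for classification.** Assume the measurement and an underlying severity are bivariate normal with correlation ρ, and that both are split at the median. Then AUROC = 0.5 + (2/π)·arcsin(ρ/√2), and the misclassified share = arccos(ρ)/π.
- ρ = 0.361: AUROC 0.66, misclassified 38%.
- ρ = 0.55: AUROC 0.75, misclassified 31%.

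**5. Sensitivity to those assumptions.**
- Split: at ρ = 0.55 the AUROC is 0.75 at the median, 0.76 with 30% above the cut, and 0.80 with 10% above it.
- Coarse grades: cutting the underlying severity into four equal-sized grades shrinks the correlation by a factor of about 0.925 (simulation). An observed 0.361 then implies 0.361/0.925 = 0.39 (AUROC about 0.68). An observed 0.55 implies 0.55/0.925 = 0.59 (AUROC about 0.78).

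**6. Precision available.** For an AUROC of 0.754 with an assumed 15 versus 15 patients, the Hanley-McNeil standard error is 0.090. The 95% CI is 0.754 ± 1.96 × 0.090 = 0.58 to 0.93.

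**7. Inflammation, text against text.**

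| Place | Outcomes named |
|---|---|
| Section 2.0, secondary goal | steatohepatitis; hepatic inflammation |
| Section 5.0, item 2, ordinal regressions | fibrosis; hepatosteatosis; steatohepatitis |
| Section 4.0, item 4.2, steatohepatitis score | steatosis (0–3) + lobular inflammation (1–3) + ballooning (0–2) |

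The inflammation score is collected but is never an outcome by itself.

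**The case against.** The best defence is that the primary goals and primary analyses agree. Both goals are worded as association, the study is called a pilot, and correlation is a reasonable first step. That stands, and it is why the correlations should stay. It does not cover the wider aim stated in sections 2.0 and 5.0, or the inflammation goal.

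Four stronger readings are tempting, and the documents support none of them.

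- *The techniques are judged only by a correlation test.* Rank correlations and ordinal regressions are also planned. What is missing is a performance measure for them.
- *A significant r is the plan's rule for declaring biopsy replaceable.* No success rule is written. The non-zero null appears only as the basis for the power statement.
- *A useless marker would pass.* A marker with zero correlation passes 5% of the time per test, and one at 0.30 to 0.40 about 36% to 60%. The correct word is could, and the documents set no benchmark for useless.
- *Inflammation is not analysed at all.* It contributes to the steatohepatitis score, which is analysed. Only a separate outcome is missing.

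It is also fair to object that adding AUROCs multiplies estimates in a plan already uncorrected for multiplicity, that a combined model fitted and assessed in the same 30 patients looks better than it is, and that an interval such as 0.58 to 0.93 will not settle substitution for biopsy. All of this is true. It shapes the fix, and it is also a reason to show the interval.

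**Conclusion.** The concern holds as a mismatch between the stated aim and what the analysis can show. The power calculation is correct.

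At n = 30, significance begins at an observed |r| of 0.361, where the interval runs from almost zero to 0.64. A result exactly at the design value of 0.55 would have an interval of 0.24 to 0.76.

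The critical value follows from the plan's own figures. The correlation intervals and pass rates also rest on the Fisher z approximation. The AUROC of about 0.75 and the 31% misclassified rest on the assumed bivariate normal model with a median split. Other splits and coarse grading move the AUROC within roughly 0.75 to 0.80. That does not change the conclusion: a study that succeeds as powered would show association and leave discrimination unmeasured.

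The missing inflammation outcome rests on the text alone and needs no assumption. Both gaps should be closed before analysis.

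**What to change.** Amend section 5.0, item 2:

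1. Add the lobular inflammation score (section 4.0, item 4.2) as an outcome in the planned ordinal regressions on kPa, %FF and both.
2. Report each correlation with its 95% CI.
3. For each ordinal regression, report a discrimination measure with 95% CI. The ordinal concordance index needs no chosen split. The alternative is AUROC at one grade boundary, fixed before data are seen. Use bootstrap optimism correction for the combined kPa and %FF model.
4. State that these are estimates with no new tests, and that a significant correlation alone supports association, not replacement of biopsy.

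The cost is a little more analysis on data already being collected, with no new patients or procedures. The intervals will be wide at n = 30 and the conclusion more modest.
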